### 3.6 Evaluation Post-Intervention:

1. All participants will record the date and time of, consistency of and pain associated with their first bowel movement, and answer whether they experienced secondary outcomes as described later.

2. Participants in the treatment arm will also log the number of prunes consumed each day.

2. Participants will be given a stamped and addressed envelope to return the data collection sheets in. Participants will receive a call from an investigator masked to the treatment allocation on postoperative day 3 inquiring about whether the participant has mailed the data collection sheets back. Those who do not answer will be called again the next day.

3. During the phone call, if the participant indicates any postoperative concerns, she will be instructed to contact the on call physician at the LAC+USC Ob/Gyn Triage.

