#### 9.0 CLINICAL AND LABORATORY EVALUATIONS AND STUDY CALENDAR

Parameter	Pre-Treatment	Postoperative day 1	Postoperative day 3*	Postoperative day 5*
Targeted history	X			
Operative history		X		
Postoperative Data Collection Sheet to be Mailed-In			X	X

\* If unable to reach patient by the telephone on postoperative day 3, another attempt will be made on postoperative day 5.

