#### 13.0 STATISTICAL CONSIDERATIONS

The sample size of 63 participants per treatment group was calculated to detect a clinically significant mean difference in time to first bowel movement of 12 hours using a two-sample t-test with a standard deviation of 23.7 at 80% power and two-sided significance level of  $p=0.05$ . The sample size was inflated to 70 participants per group to account for an estimated 10% attrition rate.

Summaries of participant characteristics will be described by treatment arm. Participant characteristics will be presented as means and standard deviations for continuous variables and counts and percentages for categorical variables. Comparisons of baseline characteristics will be assessed using two-sample t-tests or the non-parametric corollary for continuous variables and chi-square test for categorical variables. The primary outcome, a comparison of the time to first bowel movement between the treatment and control groups, will be assessed using two-sample t-tests. The secondary outcome, pain at first BM, will also be evaluated using two sample t-tests.

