**Prunes Data Collection Sheet**  
**Data collected on post op day 3**

Day of discharge to home (if discharged)  
Time of discharge to home (if discharged)

1

2

3

---

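### The primary endpoint arrives only by post: as described, the masked day 3 call checks mailing but does not record the first bowel movement, so a woman who answers but never posts has no endpoint

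*Combined protocol and SAP*

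**What the plan says.** **How the endpoint is collected.** Section 10.0 names time to first bowel movement, in hours, as the primary endpoint. In Appendix III its date and time are asked only on the self-administered survey (English and Spanish). Section 3.6 gives the return route: "Participants will be given a stamped and addressed envelope to return the data collection sheets in". The only post-treatment entry in the section 9.0 calendar is "Postoperative Data Collection Sheet to be Mailed-In".

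**What the call does.** Section 3.6 has a masked investigator telephone on postoperative day 3, "inquiring about whether the participant has mailed the data collection sheets back". The only other content described is a referral: "During the phone call, if the participant indicates any postoperative concerns, she will be instructed to contact the on call physician". The separate post op day 3 page of Appendix III asks only for the day of discharge and "Time of discharge to home (if discharged").

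**Who is called again.** Section 3.6: "Those who do not answer will be called again the next day". The section 9.0 footnote differs on the day: "If unable to reach patient by the telephone on postoperative day 3, another attempt will be made on postoperative day 5". Both cover only women who were not reached.

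**Allowance for loss.** Section 13.0: "The sample size was inflated to 70 participants per group to account for an estimated 10% attrition rate". The primary analysis is a two-sample t-test, and no method for missing times is given.

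**The concern.** The endpoint has one route into the database, and that route depends on the participant posting a form after discharge. The plan already pays for a live conversation with each woman, but as described that conversation leaves no endpoint data behind. A woman may pick up the telephone, have had her bowel movement and be able to say when. If she then does not post the sheet, she is missing from the primary analysis.

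Two things are at stake. One is power, because the margin is only seven women per arm for every cause of loss together. The other is selection: women know their arm, and return of the sheet could depend on arm or on how the bowel recovered. The documents cannot show whether that happens or in which direction, but they contain no safeguard against it.

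**Working it through.** **Inputs.** From section 13.0: difference 12 h, SD 23.7 h, two-sided 5% level, 80% power, 63 per group raised to 70 for 10% attrition. From section 1.1: 4 days +/- 1.5 days to first bowel movement without intervention. Assumed, because the documents give no figures: return rates below 90%, and the share of non-returners whose time could be obtained by telephone.

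**1. The plan's own figure.** Normal approximation: n = 2 × (1.960 + 0.842)² × 23.7² / 12² = 61.2, so 62. The exact t-test calculation gives 62.2, so 63. Then 63 / 0.90 = 70. The stated figures reproduce.

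**2. Power if sheets are not returned** (70 randomized per arm, exact t-test):

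| Not returned | Evaluable per arm | Power |
|---|---|---|
| 10% (the plan's allowance) | 63 | 80.5% |
| 20% (assumed) | 56 | 75.7% |
| 30% (assumed) | 49 | 69.9% |

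**3. How many could answer on day 3.** Treat the section 1.1 figure as roughly normal and counted from surgery. The share with a bowel movement by 72 h is Φ((3 − 4)/1.5) = Φ(−0.667) = 25%. With the planning SD of 23.7 h around the same 96 h mean it is Φ(−24/23.7) = 16%. By day 5 (120 h), the section 1.1 figure gives Φ(0.667) = 75%. Every woman here takes docusate and half also take prunes, so the true shares are unknown.

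**4. Power with telephone recovery**, at 30% non-return (21 per arm):
- A quarter recovered: 49 + 0.25 × 21 = 54.25 per arm, power about 74%.
- Half recovered: 49 + 0.5 × 21 = 59.5 per arm, power about 78%.

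These figures treat recovered times as representative, which step 5 shows is not automatic.

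**5. Why a single day 3 question is not enough.** Among non-returners it yields only times earlier than the call. Suppose a proportion l do not return, for reasons unrelated to their time, and all of them are reached at 72 h. With z = (72 − μ)/σ, the mean entering the t-test is μ − lσφ(z) / (1 − l + lΦ(z)).
- l = 0.30 in both arms, σ = 23.7, control mean 96 h: 96 − (0.3 × 23.7 × 0.239)/0.747 = 93.73.
- Prune mean 84 h: 84 − (0.3 × 23.7 × 0.351)/0.792 = 80.85. The true 12 h difference appears as 12.9 h.
- With assumed means of 72 h and 60 h, the same formula gives 11.4 h.
- With 96 h and 84 h but 30% non-return in control and 10% in the prune arm: 93.73 − 83.11 = 10.6 h. With those rates reversed: 95.38 − 80.85 = 14.5 h.

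Under these assumptions the returned sheets alone would have given 12 h without bias. The distortion comes from adding early times while the 'not yet' women stay out.

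**The case against.** The case against has four parts.

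**The wording cannot be pressed too far.** No call script is included, and the consent and contact pages are not available, so a caller might ask more than section 3.6 lists. Section 12.0 also mentions a follow-up visit. This stands as a limit: the point concerns the call as described. Nothing available contradicts that description, and the calendar assigns no data collection to such a visit.

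**Return may be good.** The plan supplies a stamped envelope and a reminder call, and 10% attrition is already covered. This stands too. A reader might infer that the trial is underpowered, but the documents do not support that. The sample size reproduces, and the 20% and 30% rates are illustrations.

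**The obvious remedy is weak.** A reader might infer that one extra question on day 3 would restore nearly all lost endpoints and reduce selection. The documents do not support that either. The section 1.1 figure suggests that most women may have nothing to report by 72 h, and step 5 shows that early times entered alone can bias the comparison. This is the strongest objection, and it changes the remedy.

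**The masking argument is thin.** A reader might infer that masking the caller is a defect because it protects no outcome. The outcome is reported by a woman who knows her arm, so having a masked person write it down removes little bias. The case for asking rests on completeness.

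**Conclusion.** The concern holds as a gap in data capture, not as an error in the sample size. On the text available, a woman who answers the day 3 call and then does not post her sheet has no further planned contact and no primary endpoint. No rule says how her missing time is handled.

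The size is uncertain. Loss up to 10% from all causes leaves 80.5% power. Beyond that, power falls below target, to about 70% at an assumed 30% non-return. A telephone back-up at that rate would bring it to about 74% (a quarter recovered) or 78% (half recovered). The quarter matches the share expected by 72 h under a rough normal reading of section 1.1. The half is an assumption with no support in the documents.

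The change should be made because it is cheap and protects the primary endpoint, but only with a repeat call and a censoring rule for women who answer 'not yet'.

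**What to change.** **Section 3.6.** On each call, the masked caller asks whether a bowel movement has occurred since surgery. She records the date and time of the first, or 'not yet' with the date and time of the call. The caller does not ask about prunes.

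**Appendix III.** Add these fields to the post op day 3 page.

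**Repeat call.** Women answering 'not yet' are called again at the later slot the calendar already has. Section 9.0 puts it on day 5 and section 3.6 on the next day, so the two must be reconciled in the same edit. On the section 1.1 figure the day 5 slot would find more women with a time to report (about 75% against 25% by day 3).

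**Section 13.0.** Use the telephone time only when no sheet is received, and flag its source. Treat a woman still 'not yet' at last contact as censored at that time in a time-to-event analysis, so that early recovered times do not enter the t-test alone. The same rule covers a returned sheet that reports no bowel movement, an answer the survey already allows.

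**Cost.** A few form fields, short additions to sections 3.6 and 13.0, about a minute per planned call, and some repeat calls. Telephone and written reports will be mixed for some women. The sample-size calculation is for a t-test, so section 13.0 would also need to say how it carries over. Women who neither post nor answer remain missing.

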## 4.0 DRUG INFORMATION

4.1 Pitted California prunes are made without preservatives or added ingredients.

4.2 Prunes will be independently purchased through in store or online retailers based on availability.

4.3 Prunes are not associated with known toxicities. They can be stored at room temperature (15°C to 30 °C).

## 5.0 SELECTION AND WITHDRAWAL OF SUBJECTIONS

### 5.1 Inclusion Criteria:

1. Female patients seen in the Gynecology or Urogynecology clinics at LAC+USC Medical Center who are planned for surgery requiring at least 24 hour stay
2. Age 18 or greater
3. Able to give informed consent
4. No contraindications to docusate or prune consumption

### 5.2 Exclusion Criteria

1. Unable to give informed consent
2. Unwilling to follow protocol
3. Active malignancy

4. Emergency surgery
5. Diabetes mellitus
6. Inflammatory bowel disease, gastroparesis, or other bowel disorder
7. History of bowel resection or presence of colostomy
8. Dependence on regular laxative use prior to surgery
9. Baseline frequency of bowel movements less than weekly
10. Intraoperative enterotomy or any bowel surgery performed at the time of surgery
11. Patient unable to initiate oral intake on post op day 1 for any reason
12. Allergy to docusate or prunes

### 5.3 Withdrawal Criteria

1. Participant request

## 6.0 STRATIFICATION/DESCRIPTIVE FACTORS/RANDOMIZATION SCHEME

6.1 Stratification factors. N/A

6.2 Descriptive factors. Age, height, weight, self-described race and ethnicity, menopausal status, baseline frequency of bowel movements, laxative use, fiber use, medications used, and baseline stool consistency.

6.3 Randomization plan:

On morning of post-operative day 1, participants who do not meet exclusion criteria will be randomized to the treatment or control group at a 1:1 ratio. Randomization blocks of 6 will be applied in this study to ensure balanced treatment assignments throughout the recruitment period. The randomization assignment list will be generated by the study statisticians. [name]. Ph.D

Participants will be standardly administered 100 g of docusate twice daily for three days per existing routine post-operative care. In addition, we will administer a total of 12 oz of prunes to the study group which are pitted and preservative free. The prunes will be provided to the participant in a sealed package. The study group be instructed to eat 4 oz of prunes daily. The control group will be advised to avoid prune products for 3 days. Each group will be given a diary to note their prune and/or docusate consumption and details of their first bowel movement.

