## 3.0 STUDY DESIGN

3.1 This is a prospective, randomized control trial.

3.2 Identification of Subjects:

All potential participants will be identified in the Gynecology or UroGynecology clinic at Los Angeles County-University of Southern California (LAC+USC) Medical Center. On average, between 8-10 patients undergo benign gynecologic surgery with overnight stay per week.

3.3 Recruitment of Participants:

Each eligible participant will be approached in person by one of the study investigators and invited to participate in the study. The informed consent will be reviewed in detail with a physician and the potential participant will be given time to ask questions. The potential participant will be allowed to take a copy of the consent home to review and discuss with family or friends.

3.4 Evaluation Pre-Intervention:

Clinical information will be collected.

3.5 Intervention:

1. Participants that undergo benign gynecologic surgery without intraoperative complications that are admitted overnight will be randomized to one of two groups.

2. Participants in the treatment arm will receive a 12 oz package of prunes on the morning of postoperative day 1.

3. All participants will receive the standard 100 g docusate sodium twice daily. Participants in the treatment arm will be instructed to consume 4 oz prunes (12 prunes) daily.

4. Additional laxatives will not be routinely given. There will be additional laxative medications (Milk of Magnesia) available for participants as needed, and it will be recorded that additional laxatives were needed.

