# Prunes Data Collection Sheet

## Data collected at time of randomization

Are any of the following exclusion criteria met?                      Yes                      No

1. Intraoperative enterotomy or any bowel surgery (not including posterior colporrhaphy) performed at the time of surgery
2. Patient unable to initiate oral intake on post op day 1 for any reason

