### If Yes to any of the above, do not randomize.

Was preoperative bowel prep administered?                      Yes                      No

Primary indication for surgery

- Adnexal mass
- Abnormal uterine bleeding (with or without fibroids)
- Fibroid uterus (without abnormal uterine bleeding)
- Pelvic organ prolapse
- Other (Please indicate) \_\_\_\_\_

Procedures performed

- Open abdominal hysterectomy
- Open sacral colpopexy
- Open surgery, other
- Vaginal hysterectomy
- Other vaginal only surgery
- Laparoscopic or robotic hysterectomy (including laparoscopic or robotic assisted vaginal hysterectomy)
- Laparoscopic or robotic sacral colpopexy
- Laparoscopic or robotic surgery, other
- Posterior colporrhaphy
- Burch urethropexy alone
- Other (Please indicate) \_\_\_\_\_

Estimated blood loss \_\_\_\_\_ ml

Surgery start time \_\_\_\_\_

Surgery end time \_\_\_\_\_

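### A single printed block size of 6, on one open unstratified list, lets someone who sees every assignment know up to a quarter of them before the last eligibility check

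*Combined protocol and SAP*

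**What the plan says.** Section 6.3 fixes the timing and the allocation: "On morning of post-operative day 1, participants who do not meet exclusion criteria will be randomized to the treatment or control group at a 1:1". It then gives one block size: "Randomization blocks of 6 will be applied in this study to ensure balanced treatment assignments throughout the recruitment period". Section 6.1 reads "6.1 Stratification factors. N/A", and section 3.2 names one medical center (two clinics), so there is a single running sequence of blocks.

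On handling the list, the text available for review says only this: "The randomization assignment list will be generated by the study statisticians". It does not say who holds the list or how each assignment is released.

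Allocation is open. Section 3.5 states: "Participants in the treatment arm will receive a 12 oz package of prunes on the morning of postoperative day 1". Section 6.3 has the control group told to keep off prune products. The only person described as masked is the day-3 telephone caller (section 3.6).

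Eligibility is completed late. Section 5.2 item 11 and the Appendix III form for data collected at randomization both list this exclusion: "Patient unable to initiate oral intake on post op day 1 for any reason". The form then instructs: "If Yes to any of the above, do not randomize".

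**The concern.** Blocking protects balance, but when the block size is fixed and known and treatment is open, the end of each block can be deduced. Once three women in a block have gone to one arm, the rest of that block is determined. With one site and no strata there is one sequence to follow.

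Consent before surgery does not close this gap, because a last eligibility check takes place at randomization. Whether a woman can start oral intake that day, with any reason counting, leaves some room for judgement. It is also plausibly related to how soon her bowels recover, and the primary endpoint is time to first bowel movement. If a slow-recovering woman were more readily judged ineligible when prunes were known to come next, the arms would differ at baseline in a way related to the outcome. A larger sample would not remove that difference.

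**Working it through.** **Inputs.** Block of 6 at 1:1, so 3 prunes and 3 control (section 6.3); no strata (6.1); 63 per group, inflated to 70 (section 13.0).

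**1. The plan's own figure.** The normal approximation gives n = 2 × (1.960 + 0.842)² × 23.7² / 12² ≈ 61.2, so 62 per group. The two-sample t-test gives 62.2, so 63, with power 0.805. Then 63 / 0.90 = 70 per group and 2 × 70 = 140 in total. The plan's figures are reproduced. They are used here only for the length of the list.

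**2. Assignments known with certainty.** There are C(6,3) = 20 equally likely blocks. An assignment is forced when one arm has already used its three places.

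| Position | 1 | 2 | 3 | 4 | 5 | 6 |
|---|---|---|---|---|---|---|
| Chance forced | 0 | 0 | 0 | 0.10 | 0.40 | 1.00 |
| Best guess correct | 0.50 | 0.60 | 0.60 | 0.70 | 0.70 | 1.00 |

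- Forced per block: 0.10 + 0.40 + 1.00 = 1.5 of 6 = 25.0%. The closed form 2m/(m+1) with m = 3 also gives 1.5.
- Over 140 (23 full blocks and 2 more): 23 × 1.5 + 0 = 34.5, and 34.5 / 140 = 24.6%.

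**3. Best guess.** The guesser always names the arm with fewer assignments so far in the block. The second row sums to 4.1, and 4.1 / 6 = 68.3%, against 50% by chance. Over 140: (23 × 4.1 + 1.1) / 140 = 68.1%.

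**4. Incomplete tracking.** Suppose the observer knows the block boundaries but sees each earlier assignment with probability p (an assumption). Certainty requires having seen all three women of the exhausted arm, so the share is 25% × p³:

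- p = 1: 25%
- p = 0.75: 10.5%
- p = 0.5: 3.1%
- p = 1/3: 0.9%

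**5. Varying block sizes.** This simulation used 800 lists of 140 and an observer who knows the set of sizes but not the boundaries. The sizes are assumed for illustration.

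| Block sizes | Certain | Best guess correct |
|---|---|---|
| 6 (as planned) | 24.6% | 68.1% |
| 4/6 | 5.5% | 69.2% |
| 4/6/8 | 2.4% | 68.0% |

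The first row agrees with the exact figures in steps 2 and 3.

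**6. Possible size of bias (assumptions only).** Suppose 10-20% of candidates are borderline on oral intake and average 24 hours slower, and every one of them is turned away when prunes are certain to come next. By symmetry this affects 25% of prune places and no control places. The prune mean then shifts by 0.25 × 24 × 0.10 = 0.6 hours to 0.25 × 24 × 0.20 = 1.2 hours, which is 5-10% of the 12-hour target. The documents give none of these inputs.

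**The case against.** The strongest reply is that a quarter is a ceiling. It requires someone who knows the block size, knows where blocks begin and has seen every earlier assignment. Recruitment runs through two clinics, any one of the investigators may approach a patient, at least one investigator is kept masked, and the documents do not say who randomizes. Step 4 shows how quickly certainty falls when tracking is partial. This stands, and the figure should be given only as an upper limit.

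A reader might infer that some 35 women would be wrongly enrolled or excluded. The documents do not support that. The figure is an expected count of deducible assignments, not of altered decisions, and the plan gives no expected number of exclusions for oral intake.

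A reader might also count the intraoperative criterion as a second discretionary call, since section 3.5 randomizes women "without intraoperative complications that are admitted overnight will be randomized". But events in surgery are settled before the morning of randomization, and the form used then asks only about enterotomy or bowel surgery, which are operative facts. Of the items on that form, only oral intake is open to judgement in the way that matters here.

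Two further objections concern the remedy. Varying the block size does not lower best-guess success for an observer who knows the set of sizes; with 4/6 it is slightly higher. That is correct. In addition, the plan already implies that exclusions are checked before randomization, so recording eligibility before release mainly enforces an existing order, and it does not stop deduction from earlier open assignments. That also stands. Neither point is a reason to keep a printed fixed size.

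**Conclusion.** The point holds as a risk of selection bias and a cheap improvement. Up to 25% of assignments per block (34.5 of 140, or 24.6%) could be known in advance by someone with complete tracking, and fewer otherwise. The route to bias is one exclusion, oral intake on day 1, and rests on two assumptions the documents neither confirm nor rule out: that whoever judges it also follows the assignments, and that borderline women recover more slowly. On the illustrative figures in step 6 the shift would be modest beside 12 hours, but it would be systematic.

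A reader might conclude that enrolment is biased, or that concealment is absent. Neither is supported. There is no evidence of biased enrolment. The available text simply does not describe how the list is held, and the title, contact and consent pages could not be checked. The sample size is unaffected.

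**What to change.** In section 6.3, replace the fixed block size with wording such as: *Assignments will be generated in randomly permuted blocks of varying size. The sizes will be held only by the study statistician and are not stated in this protocol. Each assignment will be released only after the day-1 eligibility form has been completed and recorded.* The first change removes most of the certainty, and the second prevents an eligibility decision from being revised once an assignment is seen. REDCap, already used for data (section 12.1), could hold the form and time its completion, although the documents do not say that its randomization function is set up.

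The cost is a new list and a short amendment. The other drawback is a possible final imbalance of a few women: at most half the largest block, so 4 if the largest is 8. Exact balance is not guaranteed now either, since 140 = 23 × 6 + 2 and the last two assignments can fall in the same arm (71 against 69).

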## 1.0 BACKGROUND AND HYPOTHESES

### 1.1 Background:

Postoperative constipation is among the most common complaints among women after gynecologic surgery. In the early postoperative period a temporary delay in gastrointestinal motility can be expected secondary to manual manipulation of bowel and medications including anesthesia and opiates. Postoperative constipation is a significant problem as return of bowel function is the most common reason for delayed hospital discharge after abdominal surgery. Without intervention, the average time to bowel movement after benign gynecologic and urogynecologic surgery is 4 days +/- 1.5 days. Delayed time to first bowel movement after surgery is often associated with patient discomfort and contributes to a delay in postoperative recovery.

The exact pathophysiology of delayed return of bowel function is unknown. Bayliss and Starling described the presence of inhibitory spinal reflexes acting on the bowel in 1899, which were later identified to be sympathetic inhibitory pathways in the autonomic nervous system. Sympathetic inhibition involves prevention of acetylcholine release from excitatory fibers in the myenteric plexus. The enteric nervous system has also been implicated as Holzer and Lippe suggested the role of Substance P, a neurotransmitter associated with pain. Bult et al. proposed that nitric oxide is the major inhibitory nonadrenergic noncholinergic neurotransmitter in the enteric nervous system. Hormones and neuropeptides such as vasoactive intestinal peptides, inflammation mediated by macrophages and neutrophils, general anesthesia and opioid narcotics may also contribute to the pathophysiology of delayed return to bowel function after surgery.

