## 2.0 OBJECTIVES AND PURPOSE

2.1 To determine the time to first bowel movement after benign gynecological surgery in women treated with prunes and docusate compared to those treated with docusate alone.

2.2 To determine pain associated with first bowel movement (scale 1-10), stool consistency using Bristol stool form scale, the need for additional laxatives, compliance and patient satisfaction.

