#### 10.0 CRITERIA FOR EVALUATION AND ENDPOINT DEFINITIONS

The outcome status of all eligible patients will be reported. All eligible patients who begin treatment will be included in the analysis.

Primary endpoints: Time to first bowel movement (in hours)

Secondary endpoints:

1. Stool consistency of the first bowel movement as classified by the Bristol Stool Scale (The stool types are categorical variables, and we will evaluate the differences in the frequencies of the responses by treatment status with a chi-square test)
2. Pain with bowel movement measured (Likert scale, and assessed using t-test or non-parametric methods as appropriate)
3. Satisfaction with bowel regimen (Likert scale, and assessed using t-test or non-parametric methods as appropriate)
4. Satisfaction with surgery overall (Likert scale, and assessed using t-test or non-parametric methods as appropriate)
5. Requirements for laxative (yes or no, assessed as categorical variables and evaluated by chi-square test)
6. Compliance with docusate (percentage of medications consumed, and assessed using t-test or non-parametric methods as appropriate)
7. Compliance with prunes (percentage of prunes consumed, and assessed using t-test or non-parametric methods as appropriate)

8. Adverse events of extreme bloating or flatulence (yes or no, assessed as categorical variables and evaluated by chi-square test)

Compliance with prune consumption will be defined as reported successful consumption of 2/3 of the assigned prunes.

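### The control arm's 3-day prune-avoidance advice may lapse while the primary endpoint is still open, and control prune use would go largely unrecorded

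*Combined protocol and SAP*

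**What the plan says.** - **Objective (Section 2.1, in part):** "To determine the time to first bowel movement after benign gynecological surgery in women treated with prunes and docusate compared to those treated with docusate". The sentence ends by naming docusate on its own, so the comparator is docusate without prunes.
- **Endpoint (Section 10.0):** "Primary endpoints: Time to first bowel movement (in hours"). No end of observation is given.
- **Control advice (Section 6.3):** "The control group will be advised to avoid prune products for 3 days". The start of the 3 days is not stated.
- **Randomization (Section 6.3):** allocation is 1:1 and takes place on the morning of postoperative day 1.
- **Treatment periods:** docusate is given "twice daily for three days per existing routine post-operative care". For prunes, "we will administer a total of 12 oz of prunes to the study group"; Section 7.2 lists 4 oz/day for 3 days.
- **Natural history (Section 1.1):** "Without intervention, the average time to bowel movement after benign gynecologic and urogynecologic surgery is 4 days +/- 1.5 days".
- **Recording of prune intake:** Section 6.3 gives each group a diary for prune and/or docusate use. The self-administered survey in Appendix III asks about prunes only in the study group, for days 1 to 3. The prune diary in Appendix IV has three day columns. The stool softener diary in Appendix V has five.

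**The concern.** The advice that keeps the comparator free of prunes runs by the calendar, while the endpoint runs until an event. On the protocol's own natural history, the event often comes at or after the end of the advice. A control still waiting at that point is free, as far as the visible text goes, to eat the study food, and she would be analysed as docusate alone.

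Any prunes eaten after the advice lapses and before the event could shorten control times, and so pull the difference toward zero. The exposed women are the late responders, who weigh heavily in a comparison of means. The forms would not show whether this had happened, so after a null result the explanation could be neither confirmed nor excluded.

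**Working it through.** **1. The plan's own figure.** Inputs from Section 13.0: difference 12 h, SD 23.7 (taken as hours), two-sided 0.05, power 80%. The noncentrality of the two-sample t-test at 63 per arm is 12 / (23.7 × √(2/63)) = 2.84, which gives power 80.5%. At 62 per arm it is 79.9%, so 63 reproduces. Attrition: 63 / 0.90 = 70, which also reproduces.

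**2. When the advice ends (assumption).** Counted from the morning of postoperative day 1, three days end roughly 84 to 96 h after surgery. The lower value is midnight at the end of day 3 after a midday operation. The upper value is three full days starting 24 h after surgery.

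**3. Share of controls still waiting.** Share = 1 − Φ((c − mean)/SD), where c is the hour at which the advice ends. The mean of 96 h and SD of 36 h come from Section 1.1, reading +/- 1.5 days as an SD. The SD of 23.7 h comes from Section 13.0. The 72 h mean is an assumption, because the documents give no mean for docusate alone.

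| Mean (h) | SD (h) | c = 84 h | c = 96 h |
|---|---|---|---|
| 96 | 36 | 1 − Φ(−0.333) = 63.1% | 1 − Φ(0) = 50.0% |
| 96 | 23.7 | 1 − Φ(−0.506) = 69.4% | 50.0% |
| 72 | 36 | 1 − Φ(0.333) = 36.9% | 1 − Φ(0.667) = 25.2% |
| 72 | 23.7 | 1 − Φ(0.506) = 30.6% | 1 − Φ(1.013) = 15.6% |

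A skewed (lognormal) shape with mean 96 h and SD 36 h gives 57.4% at 84 h and 42.8% at 96 h. If the 3 days were counted from surgery instead (c = 72 h), the normal model with mean 96 h and SD 36 h gives 74.8%.

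**4. Effect on power.** Diluted difference = 12 × (1 − share waiting × uptake). This credits every control who eats prunes with the full 12 h, an extreme case for prunes started that late. Uptake is an assumption. Power is from the exact t-test, 63 per arm, SD 23.7.

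| Share waiting | Uptake | Difference (h) | Power |
|---|---|---|---|
| any | 0% | 12.0 | 80.5% |
| 50% | 5% | 12 × (1 − 0.025) = 11.7 | 78.5% |
| 50% | 10% | 12 × (1 − 0.05) = 11.4 | 76.4% |
| 69.4% | 10% | 12 × (1 − 0.0694) = 11.17 | 74.7% |

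With half the gain (6 h) and 50% waiting, 5% and 10% uptake give 79.5% and 78.5%.

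**The case against.** **The design is coherent.** The advice, the prune course and the docusate course all last 3 days, so the trial can be read as comparing two 3-day regimens. This stands: there is no internal contradiction. But matching the treatment period does not protect an endpoint that outlasts it.

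**The 4-day mean may not apply to controls.** Section 1.1 labels it as without intervention, whereas controls take docusate. This stands in part. Section 1.1 cites references 3 and 4 for the figure, and Section 1.2 cites the same two for trials whose comparator was docusate alone. The documents do not settle which mean applies, so both are shown. A reader might infer that most controls will be exposed. The documents do not support that: the share is about half or more at 96 h, and below half at 72 h.

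**Uptake is unknown.** This stands. A reader might infer a serious loss of power, or that controls are told at day 3 that they may now eat prunes. No passage gives an uptake rate, and the day 3 call in Section 3.6 asks whether the sheets have been mailed. Milk of Magnesia is available as needed (Section 3.5), so prunes are not the only route to relief. Consent pages are not available for review, so the full instruction to participants cannot be checked.

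**A larger gap lies nearby.** Data collection centres on day 3, with a second call the next day (Section 3.6) or on day 5 (Section 9.0), and the t-test has no rule for women with no bowel movement yet. This is true, but it is a separate point and does not remove this one.

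**Conclusion.** The point holds as a gap in comparator integrity. The visible text permits controls to eat prunes before the endpoint, and it provides almost no record of whether they do. On the protocol's mean, 50-69% of controls could still be waiting when the advice lapses (about 43-57% under a skewed shape with SD 36 h); at an assumed 72 h mean, about 16-37%. The likely loss is modest: at 50% waiting and 5-10% uptake, power falls from 80.5% to about 76-79% even with the full 12 h gain. There is little slack, since 63 per arm is the smallest size that reaches 80%.

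Any bias runs toward no difference, so this route would not be expected to produce a false claim of benefit. What it weakens is the reading of a null result. The figures rest on assumptions about when the advice ends, the shape of the distribution, the docusate mean and the uptake.

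**What to change.** 1. **Section 6.3:** reconcile the control-arm advice with the endpoint. State when the prune-avoidance period starts, and align its length with the observation of the first bowel movement. Docusate and as-needed laxatives stay unchanged. Any limit for women with prolonged delay is for the sponsor and clinicians to set.
2. **Appendix III survey:** ask both arms whether they ate prunes, and on which day, up to the first bowel movement.
3. **Section 13.0:** add a supportive comparison of the proportion with a first bowel movement by the end of the 3-day period, when the assigned contrast is in force. Each woman's status at that time must be known, so the sheet should not be closed earlier.

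The cost is a short edit to Section 6.3 and the participant instruction, one survey line and one extra analysis. Some controls would avoid one food for somewhat longer.
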